### 3.5.6 Subgroups/Subpopulations

The following subgroups will be defined:

- Age based on age in this study:
  - For PTPs (Arm 1 and Arm 3): 0 to < 6 years,  $\geq 6$  to < 12 years,  $\geq 12$  to < 18 years and  $\geq 18$  to  $\leq 65$  years, 0 to <12 years,  $\geq 12$  to  $\leq 65$  years;
- By Region (Europe, US, Rest of the world, Asia)
- Japan subgroup

Efficacy endpoint will be analyzed by

- Positive vs. negative test for non-inhibitory Anti-Drug Antibodies (ADAs) during the Study.

The incidence of inhibitors will be summarized by

- Race (White, Black, Asian, and Other)

Annualized Bleeding Rates will be presented by

- ADA status (Positive and Negative)

For PUPs analyses for Annualized Bleeding Rates, hemostatic efficacy, TEAE and IR will be presented by inhibitor status (Positive and Negative) at the time of assessment.

CCI

Analyses by inhibitor status or inhibitor group have been defined in this SAP within relevant sections, the definition of inhibitor status and inhibitor group are the following ones:

*Inhibitor positive*

A subject is inhibitor positive if he developed a titre value (from the central lab) of at least 0.6 BU/mL, and was also confirmed in the next assessment with a titre value of at least 0.6 BU/mL.

*Inhibitor negative*

[figure not shown]
A subject is inhibitor negative if his titre value (from the central lab) was below 0.6 BU/mL.

*Inhibitor eradicated*

It refers to a subject who was previously documented with a confirmed inhibitor positive titre result and at a later point in the study, his titre value decreased and became low enough to classify him as inhibitor negative (titre value < 0.6 BU/mL). However, in order to become inhibitor eradicated, an inhibitor positive subject must first present an initial inhibitor negative titre result which must be confirmed in the next assessment by another inhibitor negative titre result.

*Inhibitor status*

A subject's inhibitor status represents a period in the study in which he is either inhibitor positive (+) or inhibitor negative (-), depending on his titre value at a given time.

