The above schema depicts a subject starting out as a negative inhibitor (-), which is the case for all subjects in the study. At some point in the study, i.e. at Time (c), his titre level went up and met the criteria for inhibitor positive status (+), which consisted of an initial titre value of  $\geq 0.6$  BU/mL, represented by (+) at Time (c), and was followed by a confirmatory titre value of  $\geq 0.6$  BU/mL in the next assessment, represented by (+)\* at Time (d). At Time (c), he is considered (+). When a subject becomes (+), the Investigator may administer an intensified prophylaxis (IP) treatment. Furthermore, he will be included in the CCI [REDACTED] to treat his inhibitory response to rVIII-SingleChain treatment. If the subject responds positively to IP and/or CCI [REDACTED], his titre values will improve (i.e. decrease) at later assessments. In the above schema, the subject became (-) at Time (e), which was followed by a confirmatory assessment (-)\* at Time (f) one month later. At Time (f), the subject is considered inhibitor eradicated.

From the above schema, we can state that:

Period of (+): Time reference after Time (c) up to Time (f), or Time (c) < Time reference  $\leq$  Time (f).

Period of (-): There will be two: on or before (+), and after (-)\*.

- On or before (+): Time (start) < Time reference  $\leq$  Time (c)
- After (-)\*: Time (f) < Time reference  $\leq$  Time (End)

By partitioning the study duration as periods of inhibitor status, analysis of time-dependent variables can be presented by inhibitor status.

*Inhibitor group*

An inhibitor group classifies a subject's inhibitor status overall during the study. Therefore, this classification is fixed for a subject, which differentiates itself from the classification by

inhibitor status for which a subject's inhibitor status may change from (-) to (+) over time according to his titre values.

The inhibitor positive group comprises of subjects who were confirmed (+) at any point during the study.

The inhibitor negative group comprises of subjects who were always (-) during the study.

For all subgroups defined in this section, in case of patients lower or equal than 3, the table will not be produced, data will only be provided in the listings.

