#### The transient inhibitor incidence

- Numerators = Number of PUPs subjects who develop inhibitors and have subsequent negative results within 6 months, i.e. 183 days
- Denominators = Total number of PUPs who develop inhibitors

A two-sided 95% exact CI for the incidence of inhibitor formation will be calculated. If zero inhibitors are observed, then a one-sided 97.5% upper confidence limit will be calculated. SAS' FREQ procedure will be applied to produce an exact CI, which uses the Clopper-Pearson CI as the default method, however, Wald CIs will also be presented. The analysis will be performed also by race.

For PUPs, the incidence (with CI) of inhibitor formation to FVIII will be estimated also by Total EDs ranges. According to the Total EDs they were exposed at time of first positive FVIII inhibitor test PUPs will be classified into 0-10 EDs, >10-25 EDs, >25-50 and >50 EDs. Assessments at EDs=0 are defined as those assessments done before date and time or on the same date and time of first dose. If time of assessment or time of first dose is missing then the inhibitor result taken at the same date of the first dose will be considered as at EDs=0. An assessment done on the same date and time of a dose will be considered to be exposed to the number of EDs the subject has been exposed before that date and time. If time is missing for the assessment or the dose, then the assessment done on the same date of dose will be considered to be exposed to the EDs the subject has been exposed before the date of that dose.

Summaries of inhibitors assay test and inhibitor titer while subjects are inhibitor positive will be provided.

The incidence of inhibitor formation to FVIII will be also summarized at the assessment of 10, 50 and 100 EDs in the current study as collected in the eCRF.

Analysis will be performed overall, by region and considering the Japanese subgroup only.

CCI

CCI

CCI

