IR will be also summarized by reason for specimen collection. If more than one assessment has the same reason, then the most recent one will be considered.

For PUPs, results will be presented overall and by inhibitor status at time of the assessment.

CCI

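### SAP 3.5.6 starts the inhibitor-positive period just after the first positive sample and ends it on the confirming negative, which contradicts its own text at both samples

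*SAP*

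**What the plan says.** SAP 3.5.6 describes a schema with four dated central-laboratory samples. The figure is not shown, but the text defines each time.

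- **(c)** is the initial titer ≥ 0.6 "BU/mL, represented by (+) at Time (c), and was followed by a confirmatory titre value of" at least 0.6 at **(d)**. The text adds "At Time (c), he is considered" positive.
- **(e)** is the first titer below 0.6, at which the text says the subject turned negative. **(f)** is the confirming negative, one month later: "At Time (f), the subject is considered inhibitor eradicated".
- The general rule in the same section is "A subject is inhibitor negative if his titre value (from the central lab) was below 0.6 BU/mL". Eradication needs a second negative at the next assessment.

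The partition then reads "Period of (+): Time reference after Time (c) up to Time (f", written out as (c) < t ≤ (f). Of the negative periods it says "There will be two: on or before (+), and after" the confirming negative. These are written out as t ≤ (c) and t > (f).

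Outputs that use the partition include AsBR and the annualized bleeding rate (ABR), hemostatic efficacy, adverse events, exposure and consumption (SAP 4.5 to 4.7). SAP 4.7.1 adds: "Summaries of inhibitors assay test and inhibitor titer while subjects are inhibitor positive will be provided".

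**The concern.** The inequalities and the prose of one section give different answers for the same samples. A programmer has to follow one or the other, and the tables will differ.

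The output most directly exposed is the titer summary while positive. A table meant to describe inhibitor titers would lose the titer that defined the inhibitor and take in titers that define its absence. For the status-split tables the issue is person-time: an interval that begins with a titer below 0.6 BU/mL is counted as positive. AsBR and treatment of major bleeds are Arm 2 primary endpoints, and the SAP presents PUP efficacy by inhibitor status as well as overall. The groups will be small, so a few misplaced samples can show.

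**Working it through.** The plan gives no figure to reproduce. The check applies the written intervals to the four schema samples and then works out the time involved.

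**Inputs**
- Intervals and meanings of (c) to (f): SAP 3.5.6.
- Gap from (e) to (f): one month in SAP 3.5.6, taken here as 28 days. The protocol's schedules of assessments define a month that way; applying it to this gap is an assumption.
- Minimum time on a status for AsBR: 8 weeks (SAP 4.6.1.1), 56 days (SAP 4.11).
- Time from (c) to (e): not given; a range is assumed.

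**Step 1: class of each sample**

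| Sample | Titer (BU/mL) | Prose of SAP 3.5.6 | Interval of SAP 3.5.6 |
|---|---|---|---|
| (c) | ≥ 0.6 | positive | negative |
| (d) | ≥ 0.6 | positive | positive |
| (e) | < 0.6 | turned negative, not yet confirmed | positive |
| (f) | < 0.6 | eradicated | positive |

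Three of the four samples are classed against their own titer.

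**Step 2: titer summary while positive**

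Suppose a subject with confirmed eradication has k samples ≥ 0.6, counting (c), and no other result below 0.6 before (e). The interval keeps k − 1 positive and 2 negative values, so the negative share is 2/(k + 1):
- k = 2: 2/3 = 67%
- k = 3: 2/4 = 50%
- k = 6: 2/7 = 29%
- k = 12: 2/13 = 15%

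A made-up example with k = 2 has titers 2.0, 1.2, 0.3 and 0.2. The interval keeps 1.2, 0.3 and 0.2, median 0.3. The positive samples are 2.0 and 1.2, median (2.0 + 1.2)/2 = 1.6. A subject who is never eradicated loses only the value at (c).

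**Step 3: positive time that follows a titer below 0.6**

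Share = 28 / (days from (c) to (e) + 28):

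| (c) to (e), days | Positive period under the SAP, days | Share |
|---|---|---|
| 28 | 56 | 50% |
| 56 | 84 | 33% |
| 168 | 196 | 14% |
| 365 | 393 | 7% |

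At (c) itself only a measurement or event at that time point moves.

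**Step 4: the 8-week minimum**

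A spell of L days from (c) to (e) counts as L + 28 days. It passes 56 days only because of the added interval when L < 56 and L + 28 ≥ 56, so for L from 28 to 55. The confirming positive (d) must lie inside that spell. With visits exactly 28 days apart, (d) falls on day 28 and (e) no earlier than day 56, and the case does not arise. It needs an early repeat sample or a visit inside its window. Protocol 8.6 asks for a repeat of any positive result as soon as possible, and monthly visits have a ± 7-day window.

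**Step 5: what does not change**

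SAP 4.7.1 defines inhibitor incidence from confirmed titers and takes the first positive result as the event. It does not use the partition. Nor does overall AsBR.

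**The case against.** The strongest defense is that holding the subject positive until the negative is confirmed is deliberate. SAP 3.5.6 says a lone negative is not enough for eradication, and the second negative period follows on from that. This stands for (e): a positive period that includes (e) is a defensible choice, even though the text says he turned negative there. It does not rescue (c), which the text calls positive, or (f), which it calls eradicated.

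It is also fair that for bleeds, adverse events and consumption the edge at (c) is close to immaterial.

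Several stronger readings are tempting, and the documents do not support them:
- **A larger inflation of positive time.** With (e) at day 112 and three-monthly confirmation at day 196, positive time would be 196/112 = 1.75 times as long. The schema puts (f) one month after (e), which gives (112 + 28)/112 = 1.25.
- **Misclassified incremental recovery.** SAP 4.7.7 plans it: "For PUPs, results will be presented overall and by inhibitor status at time of the assessment". But the readable Arm 2 schedules contain no recovery sampling, so the effect cannot be shown.
- **Misclassified anti-drug antibody results.** SAP 4.7.4.1 tabulates these by inhibitor group, which is fixed for each subject.
- **Two negatives in every subject's titers.** Only subjects with confirmed eradication have samples (e) and (f).
- **A typical positive-period median below 0.6 BU/mL.** That happens in the example because only one positive sample follows (c); a longer course need not show it.
- **Damage to the primary safety result.** Step 5 rules this out.

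**Conclusion.** The contradiction is real and sits inside one section of the SAP; nothing elsewhere in either document resolves it. The edges at (c) and (f) are wrong on the section's own text. Whether the time from (e) to (f) should be positive is a choice that the sponsor has to state.

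The certain consequence of literal application is in the titer summary: one positive value lost per positive subject, and two values below 0.6 BU/mL gained per eradicated subject. The effect on person-time is conditional. It is large for short inhibitor spells and small for long ones, as Step 3 shows, and it rests on a 28-day confirmation gap and an assumed time from (c) to (e). The 8-week effect needs the sampling pattern described in Step 4. The affected results are PUP outputs by inhibitor status or while positive. The point should be corrected before those tables are programmed, but it does not threaten the trial's main safety conclusion.

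**What to change.** In SAP 3.5.6, make the positive period closed at (c) and open at its end, so that the first positive sample is positive and the sample at (f) is negative.

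- **Preferred:** positive = (c) ≤ t < (e), where (e) is the first titer below 0.6 BU/mL that is confirmed at (f); negative = t < (c) or t ≥ (e). This agrees with the text on (e) and dates the end back to the first confirmed negative, just as onset is dated back to the first confirmed positive. Keep (f) as the date on which eradication is declared.
- **Alternative, if status is meant to hold until confirmation:** positive = (c) ≤ t < (f), with that intention stated. The (e)-to-(f) interval then stays positive by design. Titers in the summary while positive should be classed by their own result, so that the value at (e) is not summarized as positive.

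Under either rule an isolated, unconfirmed titer below 0.6 does not end the positive period; the SAP should say so.

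The cost is a few words in SAP 3.5.6 and one changed derivation in the analysis datasets. No new data are needed.

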### 3.6 Withdrawn Subjects

Subjects may withdraw, or be withdrawn, from the study for the following reasons: AEs, death, lack of efficacy, loss to follow-up, other, physician decision, protocol violation, study terminated by sponsor, or withdrawal by subject.

In addition to the general withdrawal criteria described above, PUPs in Arm 2 must be withdrawn from the study if they develop any of the following withdrawal criteria:

- Use of any FVIII product other than rVIII-SingleChain (or its marketed available version) during the study (including if used as rescue medication)
- Subject develops a confirmed high-titer inhibitor (>5 BU/mL confirmed by repeat testing at the central laboratory) but is not willing to participate in the CCI [REDACTED]
- CCI [REDACTED]

CCI [REDACTED]

### 3.7 Randomization

This is a non-randomized study.

### 3.8 Blinding

This is an open-label study.

### 3.9 Sample Size

#### Planned Number of Subjects

This study will enroll a sufficient number of subjects diagnosed with severe hemophilia A to achieve a total of least 200 PTPs with at least 100 EDs (Arms 1 and 3) and at least 50 PUPs (Arm 2).

Any subject requiring surgery during the course of the study may participate in the surgery substudy. There is no predefined target number of subjects for surgery substudy.

CCI

A large black rectangular redaction box covers the majority of the page content below the 'CCI' label.

#### Sample Size Estimation

The sample size was based on the EMA guidelines for the clinical investigation of recombinant and human plasma-derived factor VIII products [EMA, 2011]. Therefore, no sample size calculations were performed. The target enrollment is at least 200 PTPs (Arms 1 and 3) completing at least 100 EDs during enrollment in all CSL-sponsored rVIII-SingleChain studies and at least 24 PUPs (Arm 2) in this study. Thus, the study will enroll at least 224 subjects with severe hemophilia A.

## 4 Statistical Methodology

### 4.1 Planned Analyses

Statistical programming and analyses will be performed by a Contract Research Organization (PPD [REDACTED]) under the supervision of CSL Behring. Data derivations and manipulations and statistical analyses will be performed using SAS® version 9.2 or higher.

All summaries and analyses will be provided separately for PTPs and PUPs. For the separate presentation of PTPs and PUPs, all summaries and analyses will be presented as a total and by assigned treatment modality (prophylaxis, on-demand) and/or by age group for PTPs: 0 to < 6 years, ≥ 6 to < 12 years, ≥ 12 to < 18 years and ≥ 18 to ≤ 65 years, 0 to <12 years, ≥12 to ≤ 65 years.

All continuous variables will be summarized in terms of the observed sample size, mean, standard deviation, median, minimum, and maximum. Other descriptive statistics (e.g., quartiles, coefficient of variation) may be reported when appropriate. All categorical variables will be summarized using frequency counts and percentages.

Unless otherwise specified, Confidence Intervals (CIs) presented will be two-sided 95%.

Number of subjects screened will be reported. Unless otherwise stated, baseline and demographic characteristics will be summarized for the Safety, Efficacy, Surgery and C [REDACTED] populations. Note: If the Safety and Efficacy populations are equal, only the safety population should be produced and a footnote added regarding the efficacy population.

#### **Population summaries:**

- Exposure and extent of exposure will be presented for the Safety and Efficacy, Surgery and C [REDACTED] populations.
- Efficacy variables, compliance, adherence, preventive and additional doses and shift in modality will be presented for the Efficacy population.
- Dose Assignment, dose adjustments and consumption will be presented for the Safety and Efficacy population.
- Primary Efficacy will be generated for Efficacy population.
- The surgery substudy data will be analyzed and summarized for the Surgery population.
- CCI [REDACTED]
- Safety variables will be presented for the Safety population.

All listings will include arm, PUP/PTP status, and age group.

#### **4.1.1 Data Handling Conventions**

##### **4.1.1.1 Reference Date and Study Day**

Timings of all safety events, interventions, and findings will be relative to the reference date. The reference date for this study will be the date of the first dose of rVIII-SingleChain defined as the date of first dose in this study.

Day 1 is the date of the Day 1 visit for this study (see CSP schedule of assessment for details).

#### 4.1.1.2 Surgical Period

The surgical period begins when the subject receives the first dose of rVIII-SingleChain in preparation for the surgery and ends when the subject returns to the scheduled dosing regimen in the main study. If the subject does not receive rVIII-SingleChain in preparation for the surgery, then the surgical period begins on the day of surgery.

If the subject undergoes 2 surgeries, the second surgery period begins when the subject receives the first dose of rVIII-SingleChain in preparation for the second surgery, after the end of the first surgery period.

#### 4.1.1.3 CCI

CCI

#### 4.1.1.4 Baseline and Changes from Baseline

Baseline is defined as the last assessment before the first dose of rVIII-SingleChain in this study. Measurements obtained after the first dose of rVIII-SingleChain will be considered post-baseline values. If measurement of a variable is not made on a given subject before the first dose of rVIII-SingleChain, then that subject will be considered not to have a baseline value for that variable. Change from baseline will be defined as post-baseline assessment minus baseline assessment.

- CCI
- For the surgical substudy, baseline is defined as the last assessment before the first dose of rVIII-SingleChain for surgery.

#### 4.1.2 Covid-19 impact

During the course of this study, the global COVID-19 pandemic occurred. All sections with specific Covid-19 analyses described how the impacts of COVID-19 will be reported. PTPs analysis was completed when COVID-19 occurred, and therefore has no impact on PTPs. Specific COVID-19 analyses apply to the following sections:

- [4.3 Disposition of Subjects](#)
- [4.5.10 Concomitant Medication](#)
- [4.7.2 Adverse Events](#)

### 4.2 Interim Analysis

No formal efficacy or safety interim analyses are planned. In addition, safety, efficacy and / or PK data may be reported to regulatory authorities while the study is ongoing to supplement information from completed lead-in studies or the ongoing study. Those analyses do not have

an impact on the overall study design or further study conduct, and therefore are not considered to be interim analysis as defined by ICH E9.

### 4.3 Disposition of Subjects

Subject disposition will include a summary of the number of subjects screened and of screen failures (i.e., ineligible subjects who were screened).

Summaries of enrolled subjects overall and by source of enrollment will be provided on the enrolled population.

Summaries of enrolled subjects will be reported also by investigator. These will include a presentation of country, site ID, and number of subjects per site as a Total and by type of subject (PTP, PUP). In addition, the total number of sites will be presented.

The number of subjects in the following populations will be presented overall, by arm and by type of subject (PTP, PUP): Enrolled population, Safety population, Efficacy population, Surgery population, and CCI population. In addition, Efficacy population subjects who do not develop an inhibitor at any time during the study will be presented.

The number and percentage of subjects who completed/did not complete the study, and the reasons for premature withdrawal from the study will be summarized for the Safety population.

Subjects who experience either study treatment discontinuation or study discontinuation due to COVID-19 will have the reason captured in the eCRF. The reason can be either “Withdrawal by Subject,” “Physician Decision,” or “Other”. The associated free text field entry will include “COVID-19” and will be used for flagging Covid-19 reasons. When either treatment or the study is discontinued due to an AE or death, the specific corresponding AE is collected.

Cases of study treatment discontinuation or study discontinuation due to COVID-19 will be included in the summary of subject disposition by adding in a footnote indicating the patient number for the patients concerned.

The number and percentage of subjects who had any inclusion/exclusion criteria deviation will be reported for the Enrolled population. Results will be reported also by inclusion/exclusion criterion. CCI

Assessments that were missed or required alternate visit modality due to COVID-19 will be reported.

### 4.4 Baseline and Demographic Characteristics

Unless otherwise stated, demographic characteristics will be summarized for the Safety, Efficacy, Surgery and CCI populations. Demographic characteristics will include: age (as collected in the eCRF, based on age in this study), race, ethnicity, country, geographic region, height, weight, and body mass index (BMI) as a continuous and/or categorical variable. Height, weight and BMI will be based on the values at the Screening visit, i.e., the screening value from this study. BMI will be derived as  $[\text{weight (Kg)}] / [\text{height (m)}^2]$ . Treatment modality will be recorded upon entry into this study.

Baseline characteristics will be summarized for the Safety population. Baseline characteristics will include:

- Medical/surgical history summarized by System Organ Class (SOC) and Preferred Term (PT) where terms will be coded using Medical Dictionary for Regulatory Activities (MedDRA, Version 16.1 or higher). Past and active medical histories will be

displayed. Past histories are those not identified as ongoing at Screening in the current study. Active histories are those indicated as ongoing at Screening. Only the number of subjects with each history will be displayed, not the number of histories.

- Medical/surgical history related to the following viral diseases will be summarized:
  - Hepatitis B will be defined as past or active medical history mapping to a preferred term that includes “hepatitis B”, or a positive test for hepatitis B at screening.
  - Hepatitis C will be defined as past or active medical history mapping to preferred term that include “hepatitis C” or a positive test for hepatitis C at screening.
  - HIV will be defined as a past or active medical history mapping to the preferred term “HIV infection”.
- Hemophilia A history will be summarized by hemophilia A gene defect, blood group, number of spontaneous bleeding episodes in last 12 months (before the screening visit from the pivotal study for PTPs from Arm 1, previous to the screening visit in this study for PUPs in Arm 2 and for PTPs from Arm 3), number of trauma-induced bleeding episodes in last 12 months and number of bleeding episodes of unknown nature in last 12 months. For PUPs, summaries for the presence of bleeding at the screening visit will also be reported.
- FVIII treatment history, both the type of FVIII product (plasma product or recombinant product) and modality of treatment (prophylaxis, on-demand) will be summarized for PTPs. If there is more than 1 previous type of product or modality, then only the most recent one will be presented in the summary table. Subjects coming from the pivotal studies (1001, 3002) will automatically have FVIII treatment history. All previous FVIII products and associated modalities will be presented in the listings.
- Hemophilia social history and physical activity level questionnaire data will be presented in listings.

